5.2 SAFETY PARAMETERS AND DEFINITIONS

Safety assessments will consist of monitoring and recording adverse events, including serious adverse events and adverse events of special interest, performing protocol-specified safety laboratory assessments, measuring protocol-specified vital signs, and conducting other protocol-specified tests that are deemed critical to the safety evaluation of the study.

Certain types of events require immediate reporting to the Sponsor, as outlined in [Section 5.4](#).

5.2.1 Adverse Events

According to the ICH guideline for Good Clinical Practice, an adverse event is any untoward medical occurrence in a clinical investigation subject administered a pharmaceutical product, regardless of causal attribution. An adverse event can therefore be any of the following:

Pirfenidone—F. Hoffmann-La Roche Ltd

- Any unfavorable and unintended sign (including an abnormal laboratory finding), symptom, or disease temporally associated with the use of a medicinal product, whether or not considered related to the medicinal product
- Any new disease or exacerbation of an existing disease (a worsening in the character, frequency, or severity of a known condition), except *exacerbation or worsening of IPF*. *Worsening of IPF (i.e. IPF progression) is considered as an AE only in case of fatal outcome attributed to this progression (as described in [Section 5.3.5.7](#))*.
- Recurrence of an intermittent medical condition (e.g., headache) not present at baseline
- Any deterioration in a laboratory value or other clinical test (e.g., ECG, X-ray) that is associated with symptoms or leads to a change in study treatment or concomitant treatment or discontinuation from study drug
- Adverse events that are related to a protocol-mandated intervention, including those that occur prior to assignment of study treatment (e.g., screening invasive procedures such as biopsies)
- Lack of efficacy is not considered as AE

5.2.2 Serious Adverse Events (Immediately Reportable to the Sponsor)

A serious adverse event is any adverse event that meets any of the following criteria:

- Is fatal (i.e., the adverse event actually causes or leads to death)
- Is life threatening (i.e., the adverse event, in the view of the investigator, places the patient at immediate risk of death)
 - This does not include any adverse event that had it occurred in a more severe form or was allowed to continue might have caused death.
- Requires or prolongs inpatient hospitalization (see [Section 5.3.5.9](#))
- Results in persistent or significant disability/incapacity (i.e., the adverse event results in substantial disruption of the patient's ability to conduct normal life functions)
- Is a congenital anomaly/birth defect in a neonate/infant born to a mother exposed to study drug or the female partner of a male patient exposed to study drug
- Is a significant medical event in the investigator's judgment (e.g., may jeopardize the patient or may require medical/ surgical intervention to prevent one of the outcomes listed above)

Pirfenidone—F. Hoffmann-La Roche Ltd

The terms "severe" and "serious" are not synonymous. Severity refers to the intensity of an adverse event (e.g., rated as mild, moderate, or severe, or according to National Cancer Institute Common Terminology Criteria for Adverse Events [NCI CTCAE]; see [Section 5.3.3](#)); the event itself may be of relatively minor medical significance (such as severe headache without any further findings).

Severity and seriousness need to be independently assessed for each adverse event recorded on the eCRF.

Serious adverse events are required to be reported by the investigator to the Sponsor immediately (i.e., no more than 24 hours after learning of the event; see [Section 5.4.2](#) for reporting instructions).

5.2.3 Adverse Events of Special Interest (Immediately Reportable to the Sponsor)

5.2.3.1 Adverse Events of Special Interest

Adverse events of special interest are required to be reported by the investigator to the Sponsor immediately (i.e., no more than 24 hours after learning of the event; see [Section 5.4.2](#) for reporting instructions). Adverse events of special interest for this study include the following:

- Cases of potential drug-induced liver injury that include an elevated ALT or AST in combination with either an elevated bilirubin or clinical jaundice, as defined by Hy's law (see [Section 5.3.5.6](#))
- Suspected transmission of an infectious agent by the study drug, as defined below
Any organism, virus, or infectious particle (e.g., prion protein transmitting transmissible spongiform encephalopathy), pathogenic or non-pathogenic, is considered an infectious agent. A transmission of an infectious agent may be suspected from clinical symptoms or laboratory findings that indicate an infection in a patient exposed to a medicinal product. This term applies only when a contamination of the study drug is suspected.

5.2.3.2 Independent Data Monitoring Committee

An Independent Data Monitoring Committee (IDMC) will be implemented in the study. All adverse events immediately reported to the Sponsor will be reviewed by the IDMC. The IDMC will also review every death case from the point of relationship to the study drug.

The IDMC will conduct regular review of the trial safety data, with the focus on the following safety information:

Pirfenidone—F. Hoffmann-La Roche Ltd

- Death cases
- Serious adverse events
- Adverse events leading to treatment or study discontinuation
- Unexpected adverse events
- Liver enzyme increases, reported as adverse events

On the basis of the safety data aggregated from different study sites and investigators, the IDMC can recommend discontinuation of the study due to safety concerns.

IDMC members and detailed working regulations are provided in a separate document.

5.3 METHODS AND TIMING FOR CAPTURING AND ASSESSING SAFETY PARAMETERS

The investigator is responsible for ensuring that all adverse events (see [Section 5.2.1](#) for definition) are recorded on the Adverse Event eCRF and reported to the Sponsor in accordance with instructions provided in this section and in [Sections 5.4–5.6](#).

For each adverse event recorded on the Adverse Event eCRF, the investigator will make an assessment of seriousness (see [Section 5.2.2](#) for seriousness criteria), severity (see [Section 5.3.3](#)), and causality (see [Section 5.3.4](#)).

5.3.1 Adverse Event Reporting Period

Investigators will seek information on adverse events at each patient contact. All adverse events, whether reported by the patient or noted by study personnel, will be recorded in the patient's medical record and on the Adverse Event eCRF.

After informed consent has been obtained **but prior to initiation of study drug**, only serious adverse events caused by a protocol-mandated intervention should be reported (see [Section 5.4.2](#) for instructions for reporting serious adverse events).

After initiation of study drug, all adverse events will be reported until 28 days after the last dose of study drug.

For patients continuing in the rollover part of the study adverse events will be reported until Week 52.

Pirfenidone—F. Hoffmann-La Roche Ltd

120/Protocol ML39355, Version 2 dated 09-Jun-2018

Instructions for reporting adverse events that occur after the adverse event reporting period are provided in [Section 5.6](#).

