Treatment with pirfenidone will continue until Week 26 (± 1). Patients will be followed through the Follow-up visit scheduled 2-4 weeks after treatment completion or until entry into the long-term follow-up (rollover study), whichever occurs earlier. Patients who undergo lung transplantation or who chose to withdraw from study procedures early will be followed for vital status until Week 26. If patients discontinue study treatment early for any reason, they should continue with all scheduled study procedures through Week 26.

Patients who complete participation in the study prematurely due to any reasons (drop-outs) will not be replaced.

[figure not shown]
Patients who proceed until Week 26 in the study and are compliant with the study treatment, may continue treatment with commercially available pirfenidone after study completion in real clinical practice (long-term follow-up or rollover study). In this case, patients will have two follow-up assessments of FVC and 6MWT at Weeks 39 and 52 and CT scans evaluation at Week 52. Information on AEs occurrence will also be collected during the rollover part of the study.

If a patient cannot participate in the rollover part of the study for any reason, a follow-up visit will be performed 14-28 days after the last dose of pirfenidone is taken.

Pirfenidone—F. Hoffmann-La Roche Ltd

The study schema is presented in [Figure 1](#) below. A schedule of activities is provided in [Appendix 1](#).

Figure 1 Study Schema

An Independent Data Monitoring Committee (IDMC) will be implemented in the study. The IDMC will conduct regular review of the trial safety data, with the focus on death cases, serious adverse events, unexpected adverse events, adverse events leading to treatment or study discontinuation, liver enzyme increases, reported as adverse events, and other AEs immediately reported to the Sponsor (see [Section 5.2.3.2](#)).

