5.3.5.7 Deaths

All deaths that occur during the protocol-specified adverse event reporting period (see [Section 5.3.1](#)), regardless of relationship to study drug, must be recorded on the Adverse Event eCRF and immediately reported to the Sponsor (see [Section 5.4.2](#)). This includes death attributed to progression of IPF.

Death should be considered an outcome and not a distinct event. The event or condition that caused or contributed to the fatal outcome should be recorded as the single medical concept on the Adverse Event eCRF. Generally, only one such event should be reported. The term "**sudden death**" should be used only for the occurrence of an abrupt and unexpected death due to presumed cardiac causes in a patient with or without

Pirfenidone—F. Hoffmann-La Roche Ltd

preexisting heart disease, within 1 hour after the onset of acute symptoms or, in the case of an unwitnessed death, within 24 hours after the patient was last seen alive and stable. If the cause of death is unknown and cannot be ascertained at the time of reporting, "**unexplained death**" should be recorded on the Adverse Event eCRF. If the cause of death later becomes available (e.g., after autopsy), "unexplained death" should be replaced by the established cause of death.

If the death is attributed to progression of IPF, "IPF progression" should be recorded on the Adverse Event eCRF.

Deaths that occur after the adverse event reporting period should be reported as described in [Section 5.6](#).

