5.6 ADVERSE EVENTS THAT OCCUR AFTER THE ADVERSE EVENT REPORTING PERIOD

The Sponsor should be notified if the investigator becomes aware of any serious adverse event that occurs after the end of the adverse event reporting period (defined as 28 days after the last dose of study drug), if the event is believed to be related to prior study drug treatment. These events should be reported through use of the Adverse Event eCRF. However, if the EDC system is not available, the investigator should report these events directly to the Sponsor or its designee, either by faxing or by scanning and

Pirfenidone—F. Hoffmann-La Roche Ltd

emailing the Serious Adverse Event/Adverse Event of Special Interest Reporting Form using the fax number or email address provided to investigators.

5.7 EXPEDITED REPORTING TO HEALTH AUTHORITIES, INVESTIGATORS, INSTITUTIONAL REVIEW BOARDS, AND ETHICS COMMITTEES

The Sponsor will promptly evaluate all serious adverse events and adverse events of special interest against cumulative product experience to identify and expeditiously communicate possible new safety findings to investigators, IRBs, ECs, and applicable health authorities based on applicable legislation.

To determine reporting requirements for single adverse event cases, the Sponsor will assess the expectedness of these events using the following reference documents:

- Pirfenidone *Local Instruction for Use*
- Pirfenidone Core Data Sheet

The Sponsor will compare the severity of each event and the cumulative event frequency reported for the study with the severity and frequency reported in the applicable reference document.

Reporting requirements will also be based on the investigator's assessment of causality and seriousness, with allowance for upgrading by the Sponsor as needed.

Additionally, the IDMC will conduct regular review of the trial safety data, as described in [Section 5.2.3.2](#).

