8.3. Exploratory Efficacy Analyses

eCRF form: “HRCT SCAN”, “ADVERSE EVENTS”.

HRCT fibrosis score

The HRCT findings will be evaluated using HRCT scoring system. One ILD radiologist will make assessments of 4 main findings in three zones of each lung. The six zone scores will be averaged to determine the total score for each patient. Score will be recorded at the initial diagnosis and after six and 12 months in a similar manner for further comparison. The mean \pm SD of HRCT fibrosis score like continuous variable will be determined obligatory at baseline, 6 months and optional at 12 months.

The values of HRCT fibrosis score at baseline, at Week 26 and Week 52 (optional) will be summarized in table with standard descriptive statistics for continuous variables and 95% CI for the mean.

Additionally, the absolute change of HRCT fibrosis score from baseline at Week 26 and Week 52 (optional) will be summarized in table with standard descriptive statistics for continuous variables and 95% CI for the mean.

The paired t-test will be performed to evaluate the changes in the variable from the baseline to Week 26 and Week 52 (optional), respectively. The type I error rate will be set to 5%.

Lung opacity (ground-glass attenuation)

The sign ‘lung opacity’ will be qualified separately using methodology described above for other signs, and its change over time will be assessed outside the framework of a total summed index of fibrosis (HRCT fibrosis score). Lung opacity should be graded as reticular abnormality to calculate the score for each zone, i.e. the percentage (%) area of opacity in a zone should be multiplied by the score of 2.

The lung opacity score at Baseline, at Week 26 and Week 52 (optional) will be summarized using standard descriptive statistics for continuous variables and 95% CI for the mean.

Additionally, the absolute change of lung opacity score from Baseline at Week 26 and Week 52 (optional) will be summarized in table with standard descriptive statistics for continuous variables and 95% CI for the mean.

**ML39355_STATISTICAL ANALYSIS PLAN_Final 2.0_17 June 2020**Exacerbations

An exacerbation will be defined as an AE with special criteria “Is this an exacerbation of IPF?” = “Yes”, i.e. only in case the exacerbation has led to death of a patient. Rate of exacerbation will be reported in three following tables:

- Exacerbation cases during treatment period (until Week 26).

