- Exacerbation cases during long-term follow-up period (from Week 26 to Week 52).
- Exacerbation cases during whole study period (from Day 1 to Week 52, applicable only for patients continuing in the rollover study).

Exacerbation cases will be listed.

The treatment period and rollover period for the analysis of exacerbations will be defined similarly to Section 9.2.

9. Safety Analyses**9.1. Exposure**

Exposure will be evaluated based on the information from the “ASSESSMENT OF COMPLIANCE”, “STUDY DRUG ADMINISTRATION (TREATMENT PERIOD)”, “COMMERCIALY AVAILABLE PIRFENIDONE ADMINISTRATION (ROLLOVER STUDY)” eCRF form.

Pirfenidone will be taken orally in a daily dose of 2403 mg in divided doses three times per day with food. Study treatment should be titrated over 14 days, as tolerated, to the full dose of 9 capsules per day (three capsules TID), as follows:

- Days 1 to 7: one capsule TID (801 mg/day)
- Days 8 to 14: two capsules TID (1602 mg/day)
- Day 15 and continuing: three capsules TID (maximum of 9 capsules daily equal to 2403 mg/day).

Study treatment will continue until visit at Week 26 (\pm 1 week), unless terminated earlier for reasons described in Section 4.6.2 of the Protocol or patient is proceeding in the rollover study.

The total duration of exposure is defined as the time interval in weeks between the first dose and the last dose, inclusive, of study drug based on the patient study drug dosing information. Total duration (weeks) of exposure to study drug in the Treated set will be summarized by study period using descriptive statistics.

Exposure (duration of therapy during rollover study and overall up to 58 weeks) for patients in the rollover study will also be presented descriptively.

ML39355_STATISTICAL ANALYSIS PLAN_Final 2.0_17 June 2020

Descriptive statistics for Total number of capsules taken during the study period will also be presented.

All exposure data will be listed.

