9.2. Adverse Events

eCRF form: “ADVERSE EVENTS”.

AEs will be reported on a per-patient basis, i.e. counting patients rather than events.

After informed consent has been obtained but prior to initiation of study drug, only serious adverse events caused by a protocol-mandated intervention should be reported.

After initiation of study drug, all adverse events will be reported until 28 days after the last dose of study drug. Additionally, for patients continuing in the rollover part of the study adverse events will be reported until Week 52.

Only treatment emergent AEs will be summarized. In the listings, however, all occurrences of the AEs will be presented. Treatment emergent AEs will be summarized per primary SOC and PT. Severity of treatment emergent AEs will be summarized separately.

Treatment-emergent AE is any reported adverse event that starts after initiation of the study therapy and up to 28 days after the last dose of study therapy.

All registered AEs will be coded using the MedDRA version 22.0 (or further updating) and tabulated in the report with grouping by primary system organ class (SOC) and preferred term (PT).

Number (percentage) of patients and number of AEs will be presented for the Treated Set in the following tables:

- All treatment-emergent AE / SAE;
- Treatment-emergent AE / SAE related to the study drug (“Is the adverse event suspected to be caused by the study drug on the basis of facts, evidence, science-based rationales, and clinical judgment?” = “Yes” including those events where assessment is missing);
- TEAE by maximum severity (Severity, CTCAE v.4.0);
- TEAE related to study drug by maximum severity (Severity, CTCAE v.4.0);
- TEAE leading to the permanent discontinuation of study drug (Action taken with IMP=“Permanently discontinued”);
- TEAE leading to death (AE with Outcome = “Death”) including TEAE related to the study drug;
- TEAE related to the study drug leading to death;
- TEAE of special interest (“Is this an adverse event of special interest?” = “Yes”);
- Non-serious TEAEs that occurred at a frequency of $\geq 5\%$ (if no events occurred at the 5% threshold all non-serious TEAEs will be tabulated).

ML39355_STATISTICAL ANALYSIS PLAN_Final 2.0_17 June 2020

This set of tables will be repeated for the following study periods:

- Treatment period defined as first dose of study drug to last dose of study drug in the treatment period + 28 days or until the first dose in the rollover period (Treated Set).

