All Enrolled patients
Page X of X

Table with 6 columns: Patient ID/ Sex/ Age (years)/ Race, AE No/ TEAE [1]/ SAE [2], System Organ Class/ Preferred Term/ Lowest Level Term/ Reported Term, Start Date, Time/ Study Day/ End Date, Time/ Study Day/ Study period, Intermittent or persistent/ Severity/ Relationship to IMP/ Outcome, Action taken with IMP/ Concomitant medications?/ AESI?/ Exacerbation of IPF?/ Causality to concomitant medications taken. Includes placeholder text like 'XXXXXX' and 'YYYY-MM-DD HH:MM/ XXX/'.

Abbreviations: AE = Adverse Event, SAE = Serious Adverse Event, TEAE = Treatment-Emergent Adverse Event.

[1] TEAE is any reported adverse event that starts after initiation of the study therapy.

[2] Seriousness criteria: 1 = <<fatal>>, 2 = <<life-threatening>>, 3 = <<requires or prolongs in-patient hospitalization>>, 4 = <<results in persistent or significant incapacity/disability>>, 5 = <<congenital abnormality or birth defect>>, 6 = <<other significant medical event>>.

AEs are coded using MedDRA version XX.X.

Path to the program code, DDDMMYYYY, HH:MM

Date of data extraction: DDDMMYYYY

ML39355_STATISTICAL ANALYSIS PLAN_Final 2.0_17 June 2020

F. Hoffmann-La Roche Ltd
ML39355

Listing 24 Exacerbations

All Enrolled patients
Page X of X

Patient ID/ Sex/ Age (years)/ Race	AE No/ TEAE [1]/ SAE [2]/ Study period	System Organ Class/ Preferred Term/ Lowest Level Term/ Reported Term	Start Date, Time/ Study Day/ End Date, Time/ Study Day/	Intermittent or persistent/ Severity/ Relationship to Study Treatment/Outcome	Action taken with IMP/ Concomitant medications?/ AESI?/ Exacerbation of IPF?/ Causality to concomitant medications taken
XXXXXXXX/ X/ XX/ XXXXX	XX/ XXX/ XXX (X)/ XXX	XXXXXXXXXXXXXXXXXXXXXXXXXXXXXXXXXXXX/ XXXXXXXXXXXXXXXXXXXXXXXXXXXXXXXXXXXX/ XXXXXXXXXXXXXXXXXXXXXXXXXXXXXXXXXXXX	YYYY-MM-DD HH:MM/XXX/ YYYY-MM-DD HH:MM/XXX	XXXXXXXXXX/XXXXXXXXXX/ XXXXXXXXXX/XXXXXXXXXX	XXXXXXXXXX/ XXX/ XXX/ XXX/ XXXXXXXX, XXXXXXXXXXX, XXXXXXXXXX
...					

Abbreviations: AE = Adverse Event, SAE = Serious Adverse Event, TEAE = Treatment-Emergent Adverse Event.
 [1] TEAE is any reported adverse event that starts after initiation of the study therapy.
 [2] Seriousness criteria: 1 = <<fatal>>, 2 = <<life-threatening>>, 3 = <<requires or prolongs in-patient hospitalization>>, 4 = <<results in persistent or significant incapacity/disability>>, 5 = <<congenital abnormality or birth defect>>, 6 = <<other significant medical event>>.

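### Required safety reporting ends 28 days after the last dose while follow-up and death scoring run to Week 26, so a late fatal IPF event after an early stop can miss the AE tables and the exacerbation table labelled to Week 26

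*Protocol*

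**What the plan says.** **Follow-up.** Protocol 3.1: "If patients discontinue study treatment early for any reason, they should continue with all scheduled study procedures through Week 26". Section 4.6.2 repeats this in softer form, where applicable. The visit lists for Weeks 16, 20 and 26 (4.5.13.7 and 4.5.13.8) include a review of AEs and SAEs.

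**Required reporting.** Protocol 5.3.1: "After initiation of study drug, all adverse events will be reported until 28 days after the last dose of study drug". Section 5.4.2.2 sets the same limit for SAEs and AEs of special interest. Section 5.3.5.7 ties death records to it: "All deaths that occur during the protocol-specified adverse event reporting period" go on the AE eCRF, and later deaths are sent to 5.6. Section 5.6 asks for a later SAE only "if the event is believed to be related to prior study drug treatment". The extension to Week 52 is for rollover patients, who must have reached Week 26 and been compliant (3.1).

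**Death in the primary analysis.** Protocol 6.2 and SAP 6.3 and 8.1 classify a patient without a Week 26 FVC by whether death came before Week 26, whatever the date of last dose. The primary analysis scores such a death as FVC 0 mL or 0%. Deaths after lung transplant are imputed by the SSD method instead.

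**SAP windows.** Section 9.2 defines a treatment-emergent AE as one that "starts after initiation of the study therapy and up to 28 days after the last dose of study therapy", gives the treatment period the same end (or the first rollover dose), and summarises only treatment-emergent AEs. Section 8.3 labels one table "Exacerbation cases during treatment period (until Week 26", then adds: "The treatment period and rollover period for the analysis of exacerbations will be defined similarly to Section 9.2". The footnotes of Listings 23 and 24 say only "TEAE is any reported adverse event that starts after initiation of the study therapy", with no upper limit.

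**The concern.** Two clocks apply to the same patient. Efficacy, including death, runs to Week 26; required safety records run from the last dose. They separate only for patients who stop early, who may well be those with tolerability or disease problems.

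The deaths that fall between the clocks are the kind the plan expects. Protocol 6.2 presumes that deaths before Week 26 probably reflect worsening IPF. Under the causality guidance in 5.3.4, underlying disease is a reason to call an event unrelated, so 5.6 would not normally require such a death. Nor would an AE already be open, because 5.2.1 makes IPF worsening an AE only when it is fatal.

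At stake are the fatal-exacerbation table, which takes its cases from the AE form and does not cover the period on its own label, and the ability to trace a death scored in the primary analysis to a safety record.

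**Working it through.** The plan gives no figure for this gap, so there is none to reproduce. The check sets the clocks side by side and measures the difference.

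| Item | Ends at | Source |
|---|---|---|
| Visits and AE enquiry after an early stop | Week 26 | Protocol 3.1, 4.5.13.7, 4.5.13.8 |
| Death counted in the primary analysis | Week 26, any last dose | Protocol 6.2; SAP 6.3, 8.1 |
| Required AE, SAE and death records | last dose + 4 weeks | Protocol 5.3.1, 5.4.2.2, 5.3.5.7 |
| SAEs believed related | no end stated | Protocol 5.6 |
| TEAEs and treatment period | last dose + 4 weeks | SAP 9.2 |
| Table 2.17, label | Week 26 | SAP 8.3 |
| Table 2.17, period | as SAP 9.2 | SAP 8.3 |

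**Length of the gap.** For a last dose at Week s, gap = 26 - (s + 4) = 22 - s weeks, not below 0.

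- s = 4: 18 weeks
- s = 8: 14
- s = 12: 10
- s = 16: 6
- s = 20: 2
- s = 22 or later: 0
- stop near Day 1: almost 22

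The one-week allowance at the Week 26 visit can add up to 1 week. For a completer who does not roll over, Table 2.17 stays open to Week 26 + 4 = Week 30, which is 4 weeks past its label.

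**One case traced.** A patient takes the last dose at Week 10, attends Week 12, and dies of an exacerbation arising at Week 20, with no transplant. Required reporting closed at Week 10 + 4 = Week 14.

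- Tables 2.2, 2.3 and 2.6: counted (FVC 0; worst category).
- AE eCRF: no required entry unless believed related.
- Table 3.10.1: absent.
- Table 2.17: absent, although Week 20 precedes Week 26.
- Table 3.14: possible in the total row; absent from the treatment-period and rollover rows.

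**A limit on the Table 2.17 effect.** The table uses the full analysis set, which needs a post-baseline efficacy assessment; the first scheduled one is Week 12. A patient who dies before then would normally be outside the table anyway. Cases can be lost from it only between the later of Weeks s + 4 and 12, and Week 26: at most 26 - 12 = 14 weeks. Tables 3.10.1 and 3.14 use the Treated set, so the whole 22 - s applies there.

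**How many deaths.** No early-stop rate is given, so this is illustration only. Assume 5% to 20% of 60 patients stop early (3 to 12), uniformly over 26 weeks, with the 1-year mortality of 5.6% to 39.2% in Protocol Appendix 6.

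- Mean gap = 22² / (2 × 26) = 9.31 weeks.
- Person-years in the gap = 3 × 9.31 / 52 = 0.54 to 12 × 9.31 / 52 = 2.15.
- Expected deaths = person-years × [-ln(1 - mortality)]: 0.54 × 0.058 = 0.03 to 2.15 × 0.498 = 1.07.

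**Weight of one death.** Scoring 0 instead of the 65.3% in the sample-size section moves a 60-patient mean by 65.3 / 60 = 1.09 points. The plan expects a change of 65.3 - 67.8 = -2.5 and a half-width of 1.96 × 20 / √60 = 5.06, which agrees with its stated value of about 5.

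**The case against.** The strongest defence is that a window tied to exposure is a coherent choice. It is applied the same way in Protocol 5.3.1, 5.4.2.2 and 5.6 and in SAP 9.2, and in a single-arm study off-drug events have no comparator. This stands for the TEAE tables and for non-serious AEs. It does not explain Table 2.17, an efficacy output whose label and definition disagree.

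A reader might also infer several stronger points that the documents do not support.

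- *That safety reporting stops altogether.* It does not. SAEs believed related remain reportable under 5.6, and 5.3.5.7 sends late deaths there. Section 5.3.1 also has sites ask about AEs at every contact, which sits awkwardly with its own limit.
- *That late deaths fall outside all safety output.* SAP 9.2 tabulates patients who died, and Table 3.14 has a total row with no 28-day limit. Listing 1 allows death as the reason for a missing Week 26 FVC. What is missing is a named source form for a late unrelated death.
- *That the IDMC cannot see these deaths.* Protocol 5.2.3.2 has it review every death, with no 28-day limit.
- *That every death before Week 26 is scored FVC 0.* Deaths outside the full analysis set and after lung transplant are not.
- *That the primary result is wrong.* That would need a late death to be missed and the patient imputed as alive. Vital-status follow-up (3.1, for transplant and early withdrawal from procedures) and Listing 1 suggest that deaths will be known.

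The listing-footnote conflict is real but small: few late events need be recorded, and SAP 9.2 already says non-treatment-emergent events will be identified.

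**Conclusion.** The point holds within limits. After an early stop, an unrelated fatal IPF event arising more than 28 days after the last dose can count in the primary analysis without a required AE record. It is absent from Table 3.10.1 and from the treatment-period row of Table 3.14. Table 2.17 contradicts its own label: 22 - s weeks short for a stop at Week s before Week 22, and about 4 weeks long for a completer who does not roll over.

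This assumes that SAP 8.3 means what it says in borrowing the 9.2 period, and that IPF deaths are usually judged unrelated. The number affected cannot be derived from the documents and is probably small; the range of 0.03 to 1.07 deaths rests wholly on the stated assumptions. The Table 2.17 window and the recording of deaths need correction. Extending non-serious AE reporting is a preference, not an error to repair.

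**What to change.** 1. **Protocol 5.3.1, 5.3.5.7, 5.4.2.2 and 5.6.** For patients who stop early and remain in follow-up, require all deaths (including IPF progression and fatal exacerbations) and all SAEs to be recorded to the later of 28 days after the last dose and the Week 26 visit. Extending non-serious AEs is optional.
2. **SAP 8.3, Table 2.17.** Define the period by event date from first dose to Week 26, as labelled. Keep the 28-day TEAE window for the other safety tables.
3. **SAP Table 3.14.** Add a row for deaths after last dose plus 28 days and before Week 26. Adding the row will not by itself make the count equal the deaths scored in Tables 2.2 and 2.3, because Table 3.14 uses the Treated set. A footnote should reconcile them: deaths outside the full analysis set, and post-transplant deaths imputed by SSD.
4. **SAP Listings 23 and 24.** Use the 9.2 TEAE definition in the footnotes.

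**Cost.** Item 1 is a protocol amendment, which under Protocol 9.6 needs IRB/EC and, as locally required, regulatory approval before use. It also brings some off-drug events into the database. Patients who stay in follow-up already attend and are already asked about AEs. Items 2 to 4 are SAP edits, which SAP Section 2 allows until database soft lock. Without item 1, items 2 and 3 can count only the late deaths that sites happen to record.
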